#### 9.3 Treatment of AE

The patients with mild AE can continue the intervention and visits. Those with SAE should stop intervention and take corresponding treatment in time.

Once NSAE happens, the severity, duration, treatment and outcome of adverse reactions should be explained. If other drugs are used at the same time during the trial, it shall be recorded in a timely manner on case report forms.

All SAEs, whether related to the intervention or not, should be reported and recorded in the adverse event report form of the case report form, recording the occurrence time, severity, duration, measures taken, etc. Researchers have the responsibility to notify the Ethics Committee within 24 hours.

#### 10. Data management

All case report forms for each participant should be filled out by study staff in a timely manner. The case report form should be double-checked for potential errors or missing data. All data, including questionnaires, physical examinations, laboratory and other examinations, will be filled in the subject's chart. Original documents, participants' charts, and CRF forms will be stored in the study office. All data will be double-entered by researcher staff.

#### 11. Statistics

#### 11.1 Statistical power and sample size

A 12-week ICR has been reported to result in approximately 7% weight loss in overweight and obese participants, while the CCR group caused 30% less weight loss than the ICR group. According to previous studies, a 7% weight loss was approximately accompanied with a 19.3% reduction in LFC. Thus, a priori power calculation assumed 19.3% and 13.5% reduction in LFC in the ICR and CCR groups, respectively. Assuming an anticipated dropout rate of 15%, we estimated that an enrollment target of 60 participants (30 per group) would provide the trial with 80% statistical power to detect a significant difference of  $5.8\pm8\%$  in absolute LFC change between ICR and CCR group at a significance level of 0.05 using a two-tailed test.

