This 12-week, open-label, randomized, controlled, parallel-group trial was conducted at Zhongshan Hospital Fudan University between July 2020 and July 2021 (ClinicalTrials.gov, NCT04283942). The trial was initiated by the researcher, performed in accordance with the ethical principles of the Declaration of Helsinki and approved by the Ethics Committee of Zhongshan Hospital Fudan University (approval number: B2019-256). A total of 60 patients were enrolled in the trial, and written informed consent was obtained from all patients. 3.2 Randomization and masking

The simple randomization method was used to ensure similar baseline characteristics between two groups. The randomization scheme will be provided by the Statistics Department of School of Public Health of Fudan University (generated by SAS software), and randomization will be completed by staff unrelated to this trial. According to the randomization scheme, a random envelope marked with the treatment number will be made and assigned for each subject according to the order of enrollment. The treatment will be carried out according to the arrangement of corresponding scheme.

- 4. Study participants
- 4.1 Inclusion Criteria
- Age 18-70
- Diagnosed as fatty liver by ultrasound or magnetic resonance imaging
- BMI ≥ 24 kg/m^2
- Abnormal glucose metabolism: (meeting at least one):
  - Impaired glucose regulation: fasting blood glucose ≥ 100 mg/dL, postprandial blood glucose ≥ 140 mg/dL or HbA1c ≥ 5.7%
  - 2) Diabetes mellitus: diabetic symptoms + plasma glucose concentration ≥ 200 mg/dL at any time or fasting plasma glucose concentration ≥ 100 mg/dL or OGTT 2 h plasma glucose concentration ≥ 200 mg/dL

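### Section 11.1 does not say whether its liver-fat reductions and SD are relative or absolute, and on either consistent scale the stated 80% power falls to about 72% after the stated 15% dropout

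*Combined protocol and SAP*

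**What the plan says.** All of the sample size reasoning is in section 11.1. It starts from weight: about 7% loss under ICR, while "the CCR group caused 30% less weight loss than the ICR group". It links weight to liver fat by stating that "a 7% weight loss was approximately accompanied with a 19.3% reduction in LFC". From these it "assumed 19.3% and 13.5% reduction in LFC in the ICR and CCR groups, respectively". The resulting difference, 5.8 with 8 after the plus-minus sign and one percent sign for both, is then described as a difference "in absolute LFC change between ICR and CCR group at a significance level of 0.05 using a two-tailed test".

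The dropout allowance and the power claim stand in the same sentence: "Assuming an anticipated dropout rate of 15" per cent, and "an enrollment target of 60 participants (30 per group) would provide the trial with 80% statistical power".

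Two other places could have settled the scale, but neither does. Section 6.1 defines the primary outcome only as change in liver fat content. Section 11.2 models changes in continuous variables with adjustment for age, sex and baseline. On entry, section 4.1 asks for "Diagnosed as fatty liver by ultrasound or magnetic resonance imaging", with no minimum LFC. No expected baseline LFC appears anywhere.

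**The concern.** A reduction of 19.3% in a quantity measured in percent has two meanings. A patient at 20% LFC who has a 19.3% relative reduction ends at about 16.1%. A fall of 19.3 percentage points ends at 0.7%. Section 11.1 moves from reductions stated as percentages to an absolute change without a conversion and without the baseline value that a conversion would need. The SD of 8 has a percent sign and nothing else.

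This is the only justification for 60 patients, and it concerns the primary outcome. A reader cannot tell what effect the trial was sized to detect. The open scale also leaves the choice between absolute and relative change to be made after the data are seen. Separately, the 80% is quoted alongside a dropout rate, so it should hold after that dropout.

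**Working it through.** **Inputs (section 11.1 unless noted).** LFC reductions 19.3% (ICR) and 13.5% (CCR); SD 8, reading the figure after the plus-minus sign as the SD; two-sided alpha 0.05; 30 per arm, 1:1 (section 5); dropout 15%. Baseline LFC is not given and is assumed where needed.

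**1. The difference.** 0.7 × 19.3 = 13.51, and 19.3 − 13.5 = 5.8. The arithmetic is right. The standardised effect is 5.8 / 8 = 0.725. It has no units, so it is the same whether both figures are points or both are relative percent.

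**2. Reproducing the 80%, no dropout.** Normal approximation: power = Φ(5.8 / (8 × √(2/n)) − 1.96). With n = 30 the standard error is 8 × √(2/30) = 2.066, so power = Φ(2.808 − 1.96) = 80.2%. The noncentral t gives 78.8%. The required n per arm is 2 × (1.96 + 0.842)² / 0.725² = 29.9, so 30 (t: 30.9, so 31). The plan's figure is therefore the calculation with every enrolled patient analysed.

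**3. With the stated dropout.** 30 × 0.85 = 25.5 per arm, or 51 in total. The standard error is 8 × √(2/25.5) = 2.240, so power = Φ(2.589 − 1.96) = 73.5%. The noncentral t gives 71.8%. For 80% after 15% dropout, enrolment would have been 30 / 0.85 = 35.3, so 36 per arm (t: 31 / 0.85 = 36.5, so 37).

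**4. Detectable difference at 80% power, SD 8, by t.** About 5.9 with 30 per arm and 6.4 with 25.5 per arm, in whatever units the SD has.

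**5. What each scale would require.**

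- *All in percentage points.* A mean ICR fall of 19.3 points needs a mean baseline LFC of at least 19.3%. At assumed mean baselines of 20%, 25% and 30% it means removing 97%, 77% and 64% of liver fat (19.3 divided by the baseline). Power is as in steps 2 and 3.
- *All in relative percent.* Power is again as in steps 2 and 3. The word absolute is then wrong, and the primary outcome has to be relative change, which no section says.
- *Relative reductions, SD in points.* The absolute difference is 0.058 × baseline LFC. Power by t with 30 per arm analysed, and the n per arm for 80% by normal approximation:

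| Assumed baseline LFC | Difference (points) | Power | n per arm for 80% |
|---|---|---|---|
| 10% | 0.58 | 6% | 2987 |
| 20% | 1.16 | 9% | 747 |
| 30% | 1.74 | 13% | 332 |
| 40% | 2.32 | 20% | 187 |

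**The case against.** The strongest reply is that power depends only on 5.8 / 8, so any common scale returns the plan's 80%, and that a single percent sign after both figures suggests a common scale. Before dropout this is correct. A reader might infer from the change of wording that the 80% fits neither scale because the scales were mixed. That does not follow: the shortfall on a common scale comes from dropout alone.

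A reader might also infer that the absolute reading is impossible, because patients entering below 19.3% LFC cannot lose 19.3 points. But 19.3 is a group mean. The lack of an entry floor does not place the mean baseline below 19.3%. The reading is demanding and unsupported, but nothing in the documents contradicts it.

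Nor do the documents prove that 19.3% is a relative reduction. It is credited to cited studies, and the fact that weight loss is expressed relative to body weight does not fix the scale of the liver-fat figure.

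On dropout, two routes would recover about 80% at 60 enrolled. A one-sided test needs 24 per arm, or 29 after inflation, but section 11.1 states a two-tailed test. Baseline adjustment that cut the residual SD to about 7.4 (a correlation of about 0.38) would also do it, and section 11.2 does adjust for baseline. Section 11.1 does not claim such a gain, so it cannot be credited to the stated figure. Analysis by intention to treat does not restore it either: a patient lost before week 12 has no final MRI, and section 11.2 gives no method for missing outcomes.

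Finally, section 3.1 reports the trial as conducted between July 2020 and July 2021 with 60 enrolled, so rewording cannot change its power. That limits the remedy to the text, but the stated figure still needs correcting.

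**Conclusion.** The point stands in two parts.

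First, the scale of the power calculation is undefined and its wording is inconsistent: percentage reductions become an absolute change with no baseline LFC, no conversion and no source for the SD. Sections 6.1 and 11.2 do not resolve it.

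Second, the stated 80% is not delivered on either consistent scale once the plan's own 15% dropout is applied. Power is about 72% by t (73.5% by normal approximation), a shortfall of roughly 6 to 8 percentage points. This assumes that 8 is the SD of change, that 25.5 per arm provide the outcome, and that no precision is gained from covariates.

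The 6% to 20% power figures are conditional. They need relative reductions, a percentage-point SD and an assumed baseline LFC all together. They show why the scale must be stated. They are not evidence that the trial had such power, or that a null result would be uninformative.

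**What to change.** State the one scale actually prespecified for the primary outcome and use it in sections 6.1, 11.1 and 11.2.

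- If it is absolute change, give the assumed mean baseline LFC and express the expected falls in percentage points.
- If it is relative change, delete the word absolute from section 11.1 and define the outcome as relative change in section 6.1.
- In either case, give the SD and its source on that scale.
- If 5.8 and 8 are confirmed to share that scale, restate power as about 72% with 51 completers, or the detectable difference at 80% power as about 6.4 in the units of the SD. If not, recompute both from the matched figures.

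The scale must be the one fixed in advance. A new primary measure, such as a log ratio of week-12 to baseline LFC, should not be brought in now, because that would redefine the primary outcome after the trial was run. No further enrolment is called for. The cost is a few sentences in three sections and a less favourable stated power.

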#### 11.2 Data analysis

Data were analyzed according to the intention-to-treat principle using R version 4.0.3. Results are presented as means ±SD unless otherwise noted. Paired t tests or Wilcoxon matched-pairs signed-ranks tests were used for comparison of continuous variables before and after 12-week intervention. While the chi-square or Fisher's exact tests were used for comparison of the categorical variables. Generalized linear models were used to compare the changes of the continuous variables after a 12-week intervention between the two groups, with adjustment for age, sex and baseline measures. All statistical analyses were two-sided, and P<0.05 was considered statistically significant.

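### Enrolling 60 with 15% dropout gives about 72–74% power before covariate adjustment, not the stated 80%: 30 per group contains no dropout allowance

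*Combined protocol and SAP*

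**What the plan says.** Section 11.1 sets out the whole sample-size argument. Its "a priori power calculation assumed 19.3% and 13.5% reduction in LFC in the ICR and CCR groups, respectively", which gives the difference of 5.8. The final sentence begins "Assuming an anticipated dropout rate of 15" percent and goes on to say that "an enrollment target of 60 participants (30 per group) would provide the trial with 80% statistical power". The effect is printed as 5.8 ± 8% and described as a difference "in absolute LFC change between ICR and CCR group at a significance level of 0.05 using a two-tailed test".

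Section 11.2 confirms the sidedness: "All statistical analyses were two-sided, and P<0.05 was considered statistically significant". It also says that between-group comparisons of change are made "with adjustment for age, sex and baseline measures", without giving a correlation or a proportion of variance explained. Section 3.1 reports that the target was met: "A total of 60 patients were enrolled in the trial".

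**The concern.** A sample size that allows for dropout has two figures: the number who must be evaluable, and a larger number to enrol. Section 11.1 gives only one, 30 per group. It presents this as the enrolment target with dropout already considered, yet 30 is almost exactly what the formula returns with complete data. If so, the 15% is mentioned but never used.

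What is at stake is how a non-significant result would be read. The trial sets out to show that ICR is better than CCR. A reader who trusts section 11.1 would judge a null finding against a 20% chance of missing the planned effect, when that chance is higher on the plan's own inputs. The validity of the comparison itself is not affected.

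**Working it through.** **Inputs, all from section 11.1:** difference 5.8 (19.3 − 13.5); SD 8 (the figure after ±, read as the common SD of the change); two-sided 0.05; power 80%; dropout 15%; 60 enrolled, 30 per group. The standardised difference is 5.8/8 = 0.725.

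**1. Reproduce the plan's figure.** The number per group for two means is 2(z₀.₉₇₅ + z₀.₈₀)²/0.725² = 2(1.960 + 0.8416)²/0.5256 = 29.86, rounded up to 30 per group, or 60 in total. The t-test version gives 30.86. The printed 60 is therefore reproduced with zero dropout. This also supports reading ±8 as the SD. Power at 30 evaluable per group is 80.2% (normal) or 78.8% (t-test).

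**2. Apply the stated dropout.** 60 × 0.85 = 51 evaluable, or 25.5 per group. The standard error is 8 × √(2/25.5) = 2.24, and 5.8/2.24 = 2.589. Normal-approximation power is Φ(2.589 − 1.960) = Φ(0.629) = 73.5%.

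| Evaluable per group | Power, normal | Power, t-test |
|---|---|---|
| 30 (no dropout) | 80.2% | 78.8% |
| 26 | 74.3% | 72.7% |
| 25.5 (15% dropout) | 73.5% | 71.8% |
| 25 | 72.7% | 70.9% |

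Like for like, dropout costs about 7 points: 80.2% to 73.5%, or 78.8% to 71.8%.

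**3. Detectable difference with 51 evaluable.** (1.960 + 0.8416) × 2.24 = 6.28 (normal), or 6.40 (t-test), against the planned 5.8.

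**4. Enrolment that would have carried the dropout.** 30/0.85 = 35.3, so 36 per group and 72 in total. By the t-test, 31/0.85 = 36.5, so 37 per group and 74 in total.

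**5. Could a one-sided test explain the 60?** At one-sided 0.05 the number per group is 23.5 (normal) or 24.2 (t-test). Rounding the latter up to 25 and inflating gives 25/0.85 = 29.4, so 30. This fits the printed total, but sections 11.1 and 11.2 both specify two-sided testing.

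**6. What would covariate adjustment have to achieve?** For 80% power at 25.5 per group, the residual SD must fall to 7.39 (normal) or 7.25 (t-test). The variance explained is then 1 − (7.39/8)² = 0.146 or 1 − (7.25/8)² ≈ 0.18. Allowing for three further degrees of freedom used by the covariates leaves the t-test figure at about 0.18 (residual SD 7.24).

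**7. Does the scale matter?** Power depends on 5.8 and 8 only through their ratio. If both are percentage points, or both are relative percent, the results above hold unchanged. They would not hold if the two were on different scales.

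**The case against.** The strongest objection is that 72–74% describes an unadjusted comparison, whereas section 11.2 plans a model adjusted for age, sex and baseline. A multiple correlation of about 0.38 to 0.42 (the square roots of 0.146 and 0.180) would restore 80%, and the documents do not exclude that. This stands as a limit, and it is why the conclusion is confined to power before adjustment. It does not rescue the printed figure, because section 11.1 neither invokes the adjustment nor states a variance explained.

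Second, the one-sided route shows that the origin of the 60 cannot be proved: dropout might have been included and the test mislabelled. That is possible, but it contradicts the plan's two explicit statements. On the inputs as printed, the target contains no allowance.

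Third, the SD is a whole number. Had it been rounded up from 7.5, power at 25.5 per group would be 78.9% (normal) or 77.2% (t-test). At 8.49 it would be 68.4% or 66.7%. The uncertainty runs both ways, and neither end reaches 80%.

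Fourth, an intention-to-treat analysis might be said to keep all 60. Section 11.2 gives no method for missing liver fat values. Table 2 schedules MRI-PDFF and ¹H-MRS only at screening and week 12, so a participant lost before week 12 has no intermediate liver fat measurement and contributes little.

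Finally, section 3.1 describes the trial in the past tense with enrolment complete. The sample size can no longer change, and a null result should be judged mainly from its confidence interval. That bears on the form of the correction, not on whether the figure is wrong.

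**Conclusion.** The concern holds. On the inputs of section 11.1, 30 per group is the evaluable number for 80% power, so the target leaves no room for the 15% dropout assumed in the same sentence. With 51 evaluable, power before covariate adjustment is about 72–74% (70.9% to 74.3% across 25 or 26 per group and both methods), and the chance of missing a true difference of 5.8 is about 26% to 28%.

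This rests on three assumptions: that ±8 is the common SD of the change, that 5.8 and 8 are on one scale, and that participants who drop out supply no week-12 liver fat value. It concerns planned power. If fewer than 15% dropped out, the number evaluable and the power would be higher.

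A smaller fault lies in the same sentence. The 5.8 is derived from percent reductions but is called a difference in absolute change, and the unit is never stated.

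**What to change.** Correct section 11.1. As enrolment is complete, a dated correction that leaves the original calculation visible would preserve the record. It should:

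- Confirm first whether 19.3, 13.5, 5.8 and 8 are all percentage points or all relative percent, and say so.
- State that 60 were to be enrolled and about 51 evaluable after 15% dropout. This gives about 72–74% power for a difference of 5.8 with SD 8 at two-sided 0.05 before covariate adjustment or, equivalently, 80% power for a difference of about 6.3 to 6.4.
- If the adjusted model of section 11.2 is relied on to reach 80%, say so and state the variance that age, sex and baseline are assumed to explain (about 15% to 18% is needed), with its basis.

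The cost is rewording one paragraph and a less favourable stated power. No extra enrolment and no change to the analysis are needed.

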#### 11.2 Data analysis

Data were analyzed according to the intention-to-treat principle using R version 4.0.3. Results are presented as means ±SD unless otherwise noted. Paired t tests or Wilcoxon matched-pairs signed-ranks tests were used for comparison of continuous variables before and after 12-week intervention. While the chi-square or Fisher's exact tests were used for comparison of the categorical variables. Generalized linear models were used to compare the changes of the continuous variables after a 12-week intervention between the two groups, with adjustment for age, sex and baseline measures. All statistical analyses were two-sided, and P<0.05 was considered statistically significant.

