6.2 Secondary outcomes

- Change of weight
- Change of blood glucose: fasting blood glucose,2h postload blood glucose, HbA1c
- Change of liver enzymes: alanine aminotransferase, aspartate aminotransferase, γglutamyl transpeptidase
- Change of lipid profile: total cholesterol, triglyceride, high-density lipoprotein-cholesterol, low-density lipoprotein-cholesterol, free fatty acid

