6.3 Other pre-specified outcomes

- Change of fat mass and lean mass measured by a bioimpedance analyzer
- Change of abdominal adiposity measured by MRI: visceral adipose tissue and subcutaneous adipose tissue
- Change of liver stiffness measured by liver transient elastography
- Change of insulin sensitivity: fasting insulin and HOMA-IR (fasting glucose in mmol/L x fasting insulin in  $\mu$ U/mL)/22.5)
- 7. Follow-up visits
- (1) Screening visit (V0): The purpose of this visit is to confirm subjects' eligibility and interest in the proposed study, and obtain informed consent, relevant medical history (including diabetes, fatty liver, alcohol drinking history, hepatitis history, drug use, etc.), physical measurements (weight, height, waist circumference and blood pressure), and laboratory measurements (OGTT, HbA1c, liver and renal functions, electrolytes, hepatitis markers, etc). H-Proton Magnetic Resonance Spectroscopy (H-MRS), MRI-Proton Density Fat Fraction (MRI-PDFF) and liver transient elastography were applied to evaluate the fatty liver. Body composition analysis and other examinations were performed. Relevant laboratory and imaging examination results within 2 weeks before screening can be approved.
- (2) Baseline visit (V1): The baseline follow-up was scheduled within 2 weeks after the screening period. Physical examination was conducted. Subjects will be required to record their diet and steps for 3 days before day 0 and the average of calorie consumption and steps will be used as baseline reference. Randomization will be conducted.
- (3) Follow up and termination visits (V2 V9): At each visit, diet and step records will be collected. At week 2, 4, 8 12, physical measurements, fasting glucose and adverse events will be recorded. Nutritionists will provide dietary advice and help subjects to keep calorie

restriction and a balance of nutrients. On this basis, liver and renal functions, electrolytes, fasting blood glucose and lipids profiles will be measured at week 4. At week 12 (termination visit), OGTT, H-MRS, MRI-PDFF, liver transient elastography and body composition analysis will be added. At week 1, 3, 6, 10, only telephone follow-up will be conducted.

(4) Post-intervention visit (V10): At 4 weeks after the intervention (week 16), body weight will be investigated by telephone.

	Screening	Baseline								Termin ation	Post- interve ntion
Visit	V0	V1	V2	V3	V4	V5	V6	V7	V8	V9	V10

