Physical measurements: At the clinic visit, trained staff will take measurements of body weight, height, waist circumference, blood pressure according to standard procedures. Subjects should avoid wearing shoes and heavy clothes when measuring body weight. Mid-way between the lower border of rib margin and the upper border of iliac crest will be measured as waist circumference. The blood pressure will be measured after resting for 5 minutes in a sitting position and alcohol, cigarettes, coffee/tea and physical exercise will be avoided within 30 minutes before the measurement. Automatic sphygmomanometer will be applied for standardized detection.

Laboratory measurements: Blood samples will be drawn 10 hours after fasting and be used to measure blood glucose, HbA1c, liver enzymes, serum creatinine, urine acid and lipids.. High performance liquid chromatography (HPLC) method will be used for measuring HbA1c. Total cholesterol, high-density lipoprotein cholesterol, triglycerides, free fatty acids, electrolytes, liver enzymes, serum creatinine and urine acid will be measured by a model 7600 automated bioanalyzer (Hitachi, Tokyo, Japan). Low-density lipoprotein cholesterol will be calculated by the Friedewald equation. The FBG and 2-hour postprandial blood glucose in oral glucose tolerance test will be tested following a standard 75g oral glucose tolerance test and measured using the glucose oxidase method. An electrochemiluminescence immunoassay will be used to measure the fasting and 2-hour postprandial insulin. All parameters are tested in the clinical biochemical laboratory of Zhongshan Hospital affiliated to Fudan University. The clinical testing laboratory will adopt the standardized process and obtain the corresponding certification qualification.

H-MRS: Whole liver fat content by H-MRS was performed with a 1.5T MRI Scanner (Siemens Healthineers, Germany). Firstly, T1-weighted sagittal, coronal, and axial images were acquired for the localization of the spectroscopy acquisition voxel. A single 2×2×2 cm voxel was placed within the right lobe avoiding major vascular structures and subcutaneous fat tissue. The proton spectrum was acquired after shimming over the volume of interest by means of a point-resolved spectroscopy sequence with the following parameters: repetition time = 1500 ms and echo time = 135 ms. Signal intensities of the water peak at 4.8 ppm (Sw) and the fat

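### Weight and fasting glucose are measured at four post-baseline visits, but the only between-group model uses the 12-week change and gives no rule for patients without a week-12 value

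*Combined protocol and SAP*

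**What the plan says.** **Outcomes (section 6.2).** The secondary outcomes include "Change of weight" and "Change of blood glucose: fasting blood glucose,2h postload blood glucose, HbA1c", then liver enzymes and lipids. Section 6.2 gives no time point for them.

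**Schedule (section 7 and Table 2).** "At week 2, 4, 8 12, physical measurements, fasting glucose and adverse events will be recorded". Section 8 confirms that the physical measurements include weight. Table 2 places liver function and lipids at screening, week 4 and week 12. It places the OGTT, HbA1c and liver MRI-PDFF at screening and week 12 only. For weight there is one further contact: "At 4 weeks after the intervention (week 16), body weight will be investigated by telephone".

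**Analysis (section 11.2).** The one between-group model for continuous variables is given as "Generalized linear models were used to compare the changes of the continuous variables after a 12-week intervention between the two groups". Its covariates are age, sex and the baseline value. The within-group tests also compare before with after 12 weeks. The section names intention-to-treat. It contains no visit term, no within-patient correlation, no imputation or carry-forward rule, and no statement on how a patient without a week-12 value enters the model.

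**Dropout (section 11.1).** The sample size paragraph anticipates 15% dropout among 60 participants, 30 per group.

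**The concern.** A 12-week change cannot be computed for a patient who has no week-12 value. Read literally, the stated model compares completers and leaves unused up to three earlier measurements from each patient who left. Those values carry information on where the patient was heading, so leaving them out has two possible costs: some loss of precision, and bias if patients leave because of how they were responding and do so differently in the two arms.

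Outcome-related leaving is possible in this trial. It is open-label with two very different diets. Section 4.3 also ends participation for, among other things, sustained rises in fasting glucose or in ALT or AST, which are themselves secondary outcomes.

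Weight matters beyond its place in the list, because section 11.1 derives the assumed liver fat effect from an assumed weight effect.

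**Working it through.** **1. Inputs from the documents.** Section 11.1 takes 7% weight loss under ICR and 30% less under CCR:
- CCR weight loss: 7 × 0.70 = 4.9%, so the implied weight difference is 2.1 points.
- The same factor reproduces the plan's own CCR figure for liver fat: 19.3 × 0.70 = 13.5%.
- Expected leavers: 0.15 × 60 = 9, leaving 51 (25.5 per arm on average).

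The plan states no power, SD or correlation for weight or fasting glucose.

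**2. Assumptions (not in the documents).** Week-12 SD of weight change is 4 points. Correlation is 0.5 to 0.9, either equal between all visits (compound symmetry) or decaying per 4 weeks (autoregressive). For precision, dropout is random, with 5% leaving after each of weeks 2, 4 and 8.

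**3. Precision, large-sample.** Let S be the 4 × 4 correlation matrix over weeks 2, 4, 8 and 12. Per-patient information on the visit means is I = 0.85·S⁻¹ + 0.05·(M₁ + M₂ + M₃), where Mₖ is the inverse of the leading k × k block of S, padded with zeros. The week-12 variance, in units of σ²/60, is the last diagonal element of I⁻¹. Completers-only gives 1/0.85 = 1.176. Effective N is 60 divided by the variance.

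| Structure | Correlation | Variance, all visits | Effective N (v 51) | Reduction v 1.176 |
|---|---|---|---|---|
| Autoregressive | 0.5 | 1.155 | 52.0 | 1.8% |
| Autoregressive | 0.7 | 1.122 | 53.5 | 4.7% |
| Autoregressive | 0.9 | 1.054 | 56.9 | 10.4% |
| Compound symmetry | 0.5 | 1.119 | 53.6 | 4.9% |
| Compound symmetry | 0.7 | 1.077 | 55.7 | 8.5% |
| Compound symmetry | 0.9 | 1.027 | 58.4 | 12.7% |

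**4. Precision, simulated at 30 per arm.** With about 15% random dropout, completers-only variance is about 0.5%, 3%, 6% and 10% higher at 4-week correlations of 0.5, 0.7, 0.8 and 0.9. The largest simulated ratio at 0.9 is (1.113/1.040)² = 1.15. Since 1/1.15 = 0.87, that is 13% lower variance with all visits. The overall range is therefore about 0% to 13% lower. The ceiling is 15% lower (1 - 0.85), reached only if earlier visits predicted week 12 perfectly.

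**5. Bias, simple bound for one arm.** Suppose the 15% of one arm with the worst early change all leave. The mean early change of those who stay shifts by φ(1.036)/0.85 = 0.233/0.85 = 0.274 SD in that arm's favour. The week-12 mean shifts by the correlation times this: 0.5 × 0.274 = 0.14 SD, up to 0.9 × 0.274 = 0.25 SD.

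**6. Bias, simulated.** Assume about 19-20% ICR v 10% CCR dropout, with poor ICR responders, judged on recorded weights, leaving more. The true difference is -2.10. Over correlations of 0.5 to 0.9:
- Completers-only estimate: about -2.35 to -2.75, an error of 0.25 to 0.65 points (0.25/2.10 = 12% to 0.65/2.10 = 31%).
- All-visits likelihood estimate: about -2.1 throughout.
- Standard error of the completers-only difference: about 4 × √(2/25.5) = 1.12. The error is therefore roughly 0.2 to 0.6 of a standard error.

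**The case against.** **Exclusion is not stated.** A reader might infer that the plan drops early leavers. It does not say so: it names intention-to-treat, and recall for the week-12 visit, imputation or carry-forward would all be compatible with the text. What stands is that none of these is specified, and that the model as written needs a week-12 value.

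**The stated model is a standard one.** A baseline-adjusted comparison of 12-week change is an accepted analysis of a week-12 endpoint. That is true, so this is an available improvement and not an error.

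**The precision gain is small.** It approaches 13% only at correlations near 0.9. At 0.5 to 0.7 with decaying correlation it is a few percent at most. This objection stands in full.

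**The bias scenario is chosen.** A reader might infer that the weight result is biased towards ICR. The documents give only an overall 15%. The split between arms and the response-related leaving are assumptions, and the repeated-measures estimate recovers the truth because leaving was made to depend on recorded values. The direction holds at every correlation tried, but the error stays below one standard error.

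**A mixed model is not intention-to-treat.** Under missing at random it predicts week 12 as though leavers had continued like similar patients who stayed. It does not estimate what happened to those who stopped the diet. So the case for it rests on using more of the randomised patients' data, not on meeting the intention-to-treat statement.

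**Scope is limited.** Liver enzymes and lipids have one intermediate visit, so there is less to recover. Patients who leave before week 2 contribute no post-baseline value under either model.

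**Conclusion.** The point holds as a low-cost improvement to the analysis of secondary outcomes. The schedule provides repeated values, the only between-group model uses the last one, and no rule covers its absence. At the plan's own dropout rate, about 9 of 60 patients would be missing from these comparisons unless they are recalled or imputed.

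The precision gain is minor. The better reason for the change is protection against bias if leaving depends on recorded response and differs by arm, worth roughly 0.25 to 0.65 points on an assumed 2.10-point weight difference in the scenario examined. These sizes rest on the assumed SD, correlation and dropout pattern. The documents do not show that such dropout occurred or would occur.

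Nothing here extends to the primary outcome. Liver fat content has no intermediate measurement, so a repeated-measures model would recover nothing for it.

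**What to change.** In section 11.2, for weight and fasting glucose, and also for liver enzymes and lipids (with less to gain), specify a mixed model for repeated measures:
- all scheduled post-baseline visits to week 12;
- arm × visit and baseline × visit, with age and sex;
- unstructured covariance, with a named fallback if it does not converge;
- the week-12 contrast between arms, with its 95% CI, as the reported result.

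State the missing-at-random assumption, and say whether patients who leave early are asked back for the week-12 measurements. Keep the baseline-adjusted generalized linear model for outcomes measured only at baseline and week 12.

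The cost is a few sentences and a little more R code, with no new data. The downside is a slightly more complex model that relies on missing at random. Section 11.2 is written in the past tense. If the analysis is already complete, the same model can be reported as a sensitivity analysis beside the week-12 comparison.
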